6.6.1. General Guidelines for Immune-Related Adverse Events

AEs associated with immunotherapy treatment may be immune-mediated. These immune-related AEs (irAEs) may occur shortly after the first dose or several months after the last dose of treatment, or during the treatment course, and may affect more than one body system simultaneously. Therefore, early recognition of and initiation of treatment for these events is critical to reduce potential complications. Based on existing data from the study 204691, most treatment-related AEs were Grade 1 or 2, managed with supportive care and if appropriate the administration of corticosteroids.

For suspected irAEs, ensure adequate evaluation to confirm the etiology or exclude other causes. Additional procedures or tests such as, but not limited to, bronchoscopy, endoscopy, or skin biopsy may be included as part of the evaluation. Based on the severity of irAEs, withhold or permanently discontinue treatment and administer corticosteroids. Dose modification and toxicity management guidelines for irAEs associated with immunotherapies are provided in Table 6.

Before administration of study treatment, investigators are to review a participant's AEs, concomitant medications, and clinical evaluation results, e.g., vital signs, laboratory results, ECOG PS, physical examination findings, responses, etc. as outlined in the Schedule of Activities (Table 1) to monitor for new or worsening irAEs and ensure continues dosing is appropriate.

Adverse Events of Special Interest (AESI)

AESI are defined as events of potential immunologic etiology, including irAEs. Such events recently reported after treatment with other immune modulatory therapy include colitis, uveitis, hepatitis, pneumonitis, diarrhea, endocrine disorders, and specific cutaneous toxicities, as well as other events that may be immune mediated.

Table 6 Dose Modification and Toxicity Management Guidelines for Immune-Related AEs

General instructions:

- Corticosteroid taper should be initiated upon irAE improving to □ Grade 1 and continue to taper over at least 4 weeks.

- For situations where immunotherapy treatment has been withheld, treatment can be resumed after irAE has been reduced to □ Grade 1 and corticosteroid has been tapered. Immunotherapy treatment should be permanently discontinued if irAE does not resolve or corticosteroids cannot be reduced to ≤10 mg prednisone or equivalent per day within 12 weeks of last dose of study treatment.
- For severe and life-threatening irAEs, IV corticosteroid should be initiated first followed by oral steroid. Other immunosuppressive treatment should be initiated if irAEs cannot be controlled by corticosteroids.

Immune-related AEs	Severity Grade or Condition (CTCAEv5.0)	Action Taken to ^a : GSK3359609/ Pembrolizumab	Management: Corticosteroid and/or Other Therapies	Monitoring and Follow-up
Respiratory				
Pneumonitis	Grade 2	Withhold	
 • Administer corticosteroids (initial dose of 1-2 mg/kg prednisone or equivalent) followed by taper • Add prophylactic antibiotics for opportunistic infections 	
 • Monitor participants for signs and symptoms of pneumonitis. • Evaluate participants with suspected pneumonitis with radiographic imaging and initiate corticosteroid treatment.
	Grade 3 or Grade 4, or recurrent Grade 2	Permanently discontinue		
Gastrointestinal				
Diarrhea / Colitis	Grade 2 or Grade 3	Withhold	
 • Administer corticosteroids (initial dose of 1-2 mg/kg prednisone or equivalent) followed by taper 	
 • Monitor participants for signs and symptoms of enterocolitis (i.e., diarrhea, abdominal pain, blood or mucus in stool with or without fever) and of bowel perforation (i.e., peritoneal signs and ileus). • Participants with ≥ Grade 2 diarrhea suspecting colitis should consider GI consultation and performing endoscopy to rule out colitis. • Participants with diarrhea/colitis should be advised to drink liberal quantities of clear
	Grade 4 or recurrent Grade 3	Permanently discontinue		

Immune-related AEs	Severity Grade or Condition (CTCAEv5.0)	Action Taken to ^a : GSK3359609/ Pembrolizumab	Management: Corticosteroid and/or Other Therapies	Monitoring and Follow-up
				fluids. If sufficient oral fluid intake is not feasible, fluid and electrolytes should be substituted via IV infusion.
Hepatobiliary				
AST / ALT elevation or increased bilirubin	Grade 2	Withhold	
 Administer corticosteroids (initial dose of 0.5-1 mg/kg prednisone or equivalent) followed by taper 	
 Monitor with liver function tests (consider weekly or more frequently until liver enzyme value returned to baseline or is stable).
	Grade 3 or Grade 4	Permanently discontinue	
 Administer corticosteroids (initial dose of 1-2 mg/kg prednisone or equivalent) followed by taper 	
 Refer to Section 10.8 for liver safety required actions and follow-up assessments and study treatment guidelines.
Endocrine				
Type 1 diabetes mellitus (T1DM) or Hyperglycemia	New onset T1DM or Grade 3 or Grade 4 hyperglycemia associated with evidence of β -cell failure	Withhold ^b	
 Initiate insulin replacement therapy for participants with T1DM Administer anti-hyperglycemic in participants with hyperglycemia 	
 Monitor participants for hyperglycemia or other signs and symptoms of diabetes.
Hypophysitis	Grade 2	Withhold	
 Administer corticosteroids and initiate hormonal replacements as clinically indicated. 	
 Monitor for signs and symptoms of hypophysitis (including hypopituitarism and adrenal insufficiency).
	Grade 3 or Grade 4	Withhold or permanently discontinue ^b		
Hyperthyroidism	Grade 2	Continue	
 Treat with non-selective beta-blockers (e.g., propranolol) or thionamides as appropriate 	
 Monitor for signs and symptoms of thyroid disorders.
	Grade 3 or Grade 4	Withhold or Permanently discontinue ^b		
Hypothyroidism	Grade 2, Grade 3, or Grade 4	Continue	
 Initiate thyroid replacement hormones (e.g., 	
 Monitor for signs and symptoms of thyroid disorders

Immune-related AEs	Severity Grade or Condition (CTCAEv5.0)	Action Taken to ^a : GSK3359609/ Pembrolizumab	Management: Corticosteroid and/or Other Therapies	Monitoring and Follow-up
			levothyroxine or liothyronine) per standard of care	
Renal				
Nephritis: Grade according to increased creatinine or acute kidney injury	Grade 2	Withhold	
 Administer corticosteroids (prednisone 1-2 mg/kg or equivalent) followed by taper 	
 Monitor changes of renal function
	Grade 3 or Grade 4	Permanently discontinue		
Cardiovascular				
Myocarditis	Grade 2	Permanently discontinue	
 Based on severity of AE administer corticosteroids 	
 Ensure adequate evaluation to confirm etiology and/or exclude other causes.
	Grade 3 or Grade 4			
Neurological				
Neurological Toxicities	Grade 2	Withhold	
 Based on severity of AE administer corticosteroids 	
 Ensure adequate evaluation to confirm etiology and/or exclude other causes
	Grade 3 or Grade 4	Permanently discontinue		
Skin				
Exfoliative Dermatologic Conditions	Suspected SJS, TEN, or DRESS	Withhold	
 Based on severity of AE administer corticosteroids 	
 Ensure adequate evaluation to confirm etiology and/or exclude other causes
	Confirmed SJS, TEN, or DRESS	Permanently discontinue		
Other				
All other immune-related AEs	Grade 3, or intolerable/persistent Grade 2	Withhold or discontinue based on the type of event ^c	
 Based on severity of AE administer corticosteroids 	
 Ensure adequate evaluation to confirm etiology or exclude other causes
	Grade 4 or recurrent Grade 3	Permanently discontinue		

Abbreviations: AE=adverse events; ALT=alanine aminotransferase; AST= aspartate aminotransferase; CTCAE=common terminology criteria for adverse events; DRESS=Drug Rash with Eosinophilia and Systemic Symptom; GI=gastrointestinal irAE=immune-related AE; IV=intravenous; kg=kilogram; mg=milligram; SJS=Stevens-Johnson Syndrome; T1DM=Type 1 diabetes mellitus; TEN=toxic epidermal necrolysis

- The actions taken for GSK3359609 infer an action required for placebo due to the blinded design. The actions taken for GSK3359609/pembrolizumab includes chemotherapy.
- The decision to withhold or permanently discontinue study treatment is at the discretion of the investigator or treating physician. If control is achieved or ≤Grade 2, study treatment may be resumed.
- The events that require discontinuation include but are not limited to: encephalitis, and other clinically important irAEs (e.g., vasculitis and sclerosing cholangitis).

6.6.2. Dose Modification and Toxicity Management of Infusion-Related Reactions Related to Immunotherapy Treatment

Infusion reactions are a well-documented AE associated with the administration of mAb. Infusion reactions typically develop within 30 minutes to 2 hours after initiation of drug infusion, although symptoms may be delayed for up to 48 hours. The incidence of infusion reactions varies by mAb agent, and there are multiple mechanisms known to lead to infusion-related reactions including both IgE-dependent anaphylactic and non-IgE dependent anaphylactoid hypersensitivities. Cytokine release syndrome, and when severe, cytokine “storm”, has been identified as a sequela of the immune system activation associated with infusion reactions.

Infusion reactions may affect any organ system in the body; most are mild in severity, although severe and even fatal reactions occur. As a group, infusion reactions (including both cytokine-mediated and allergic) usually occur during or within a few hours of drug infusion. Occasionally, a reaction may occur 1 to 2 days after administration. The NCI-CTCAE (version 5.0) for grading adverse reactions during chemotherapy administration has a scale for grading the severity of infusion reactions and separate grading scales for allergic reactions and anaphylaxis. While use of these separate grading scales may be useful for classifying the nature of an infusion reaction for research purposes, they are less useful for clinical care, since it may not be obvious if the participant is having an allergic infusion reaction or a non-allergic infusion reaction.

Clinically, an infusion reaction may present with flushing, itching, urticaria, and/or angioedema, repetitive cough, sudden nasal congestion, shortness of breath, chest tightness, wheeze, sensation of throat closure or choking, and/or change in voice quality, faintness, tachycardia (or less often bradycardia), hypotension, hypertension and/or loss of consciousness, nausea, vomiting, abdominal cramping, and/or diarrhea, sense of impending doom, tunnel vision, dizziness, and/or seizure, severe back, chest, and pelvic pain. Refer to [Table 8](#) for dose modification and treatment guidance for immunotherapy infusion reactions.

To better understand the underlying etiology of these events, serum tryptase, C-reactive protein (CRP), ferritin, and a cytokine panel should be drawn during the occurrence of an infusion reaction/CRS of any grade as outlined in [Table 7](#). The serum tryptase, CRP and ferritin panels should be performed at the investigator’s designated local laboratory. The serum cytokine panel will be performed at a GSK designated laboratory. These data will aid in the classifying (albeit retrospectively) the etiology of the AE.

Table 7 Infusion-Related Reaction Laboratory Panel

Analyte	Relationship to Adverse Event
Serum tryptase ^a	IgE-related infusion reaction (Allergic/anaphylaxis) [Schwartz, 2006]
Serum CRP ^a	Elevated in CRS [Lee, 2014]
Serum ferritin ^a	Elevated in CRS [Lee, 2014]
Serum cytokine panel ^b (IFNγ [*] [^] , TNFα [*] [^] , IL1β , IL2*, IL4, I-6* [^] , IL8* , IL10*, IL12p70 , and IL13)	* Reported to be elevated in CRS [Lee, 2014] ^ Consistently reported as elevated in CRS [Lee, 2014]

Abbreviations: CRP = C-reactive protein; CRS = Cytokine release syndrome; IFN γ = Interferon gamma; TNF α = Tumor necrosis factor alpha; IL = Interleukin.

- Performed by investigator designated local laboratory if available; otherwise performed by GSK designated laboratory.
- Performed by a GSK designated laboratory; note: in participants enrolled from China sites, only the analytes **bolded** and *italicized* will be tested.

The guidelines provided in Table 8 are suggestions. Investigators and site staff may also follow their site standard operating procedures for the treatment of these events.

Table 8 Infusion Reaction Dose Modification and Treatment Guidelines

NCI CTCAE Grade	Treatment	Premedication at Subsequent Dosing
Grade 1 Mild reaction; infusion interruption not indicated; intervention not indicated	
 Increase monitoring of vital signs as medically indicated until the participant is deemed medically stable in the opinion of the investigator. 	
 None
Grade 2 Requires therapy or infusion interruption but responds promptly to symptomatic treatment (e.g., antihistamines, NSAIDs, narcotics, IV fluids); prophylactic medications indicated for ≤ 24 hrs.	
 Stop Infusion Additional appropriate medical therapy may include but is not limited to: 
 IV fluids Antihistamines NSAIDs Acetaminophen Narcotics Increase monitoring of vital signs as medically indicated until the participant is deemed medically stable in the opinion of the investigator If symptoms resolve within 1 hour of stopping drug infusion, the infusion may be restarted at 50% of the original infusion rate (e.g. from 100 mL/hr to 50 mL/hr). Otherwise dosing will be held until symptoms resolve and the participant should be premedicated for the next scheduled dose 
Participants who develop Grade 2 toxicity despite adequate
	
 Participant may be premedicated 1.5hr (± 30 minutes) prior to infusion of study drugs with: 
 Diphenhydramine 50 mg po (or equivalent dose of antihistamine). Acetaminophen 500-1000 mg po (or equivalent dose of analgesic).

NCI CTCAE Grade	Treatment	Premedication at Subsequent Dosing

Grades 3 or Grade 4 Grade 3: Prolonged (i.e., not rapidly responsive to symptomatic medication and/or brief interruption of infusion); recurrence of symptoms following initial improvement; hospitalization indicated for other clinical sequelae (e.g., renal impairment, pulmonary infiltrates) Grade 4: Life-threatening; pressor or ventilatory support indicated
	
premedication should be permanently discontinued from further study treatment
 
 • Stop Infusion • Additional appropriate medical therapy may include but is not limited to: 
 ○ Epinephrine** ○ IV fluids ○ Antihistamines ○ NSAIDs ○ Acetaminophen ○ Narcotics ○ Oxygen ○ Pressors ○ Corticosteroids • Increase monitoring of vital signs as medically indicated until the participant is deemed medically stable in the opinion of the investigator • Hospitalization may be indicated. 
**In cases of anaphylaxis, epinephrine should be used immediately. Participant is permanently discontinued from further study treatment.
	
 • No subsequent dosing

Note: Appropriate resuscitation equipment should be available at the bedside and a physician readily available during the period of drug administration. For further information, please refer to the Common Terminology Criteria for Adverse Events v5.0 (CTCAE) at http://ctep.cancer.gov
		

Abbreviations: CTCAE=common terminology criteria for adverse events; hr=hour; IV=intravenous; mg=milligram; ml=millilitres; NSAID=nonsteroidal anti-inflammatory drug; po=per os [by mouth]

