6.6. Dose Modification

Distinct safety management guidelines, including dose modification algorithms, are provided in this section for:

- GSK3359609
- Pembrolizumab

Refer to chemotherapy prescribing information or standard practice guidelines for the management of chemotherapy-related AEs or potential safety-related issues; including resuming chemotherapy treatment and dose reductions following recovery of AE.

Please note: In instances where the investigator is directed to permanently discontinue study treatment, the instructions are mandatory as described in Section 7.1.

All AEs are to be graded according to NCI-CTCAE (version 5.0) [NCI, 2017]. All dose modifications and the reason(s) for the dose modification must be documented in the eCRF.

Refer to pembrolizumab prescribing information [KEYTRUDA, 2019] or IB [Merck, 2021] for additional information regarding the background and the management of other AEs or potential safety-related issues. The investigator may consult the GSK Medical Monitor on study treatment modifications (i.e., holds or discontinuation) or on the management of AEs.

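### Section 6.6.2 labels all of Table 8 as suggestions, although its two permanent-discontinuation entries are mandatory under Section 6.6

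*Protocol*

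**What the plan says.** Four parts of the protocol bear on this.

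- **Section 6.6 (Dose Modification)** sets the general rule: "In instances where the investigator is directed to permanently discontinue study treatment, the instructions are mandatory as described in Section 7.1".
- **Section 7.1** lists unacceptable toxicity among the events that end study treatment and refers the reader to Section 6.6 with its subsections, which takes in 6.6.2.
- **Section 6.6.2**, immediately before Table 8, states: "guidelines provided in Table 8 are suggestions. Investigators and site staff may also follow their site standard operating procedures for the treatment of these events".
- **The table itself** (Table 8) is titled "Infusion Reaction Dose Modification and Treatment Guidelines", and the text of 6.6.2 sends the reader to it "for dose modification and treatment guidance for immunotherapy infusion reactions". In the Grade 2 row, participants whose Grade 2 toxicity develops in spite of adequate "premedication should be permanently discontinued from further study treatment". In the Grade 3/4 row, the treatment column ends "Participant is permanently discontinued from further study treatment" and the premedication column reads "No subsequent dosing".

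**The concern.** One section gives the same two instructions opposite status. Section 6.6 makes a directed permanent stop binding. The sentence above Table 8 turns the whole table into advice and exempts nothing. Site staff managing a reaction will have Table 8 and the sentence above it in front of them, not the general note at the start of Section 6.6.

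The stake is participant safety. Section 6.6.2 itself acknowledges that infusion reactions can be severe or fatal. A site that took the label at face value could go on dosing a participant who has had a Grade 2 reaction under premedication. The SAP (Section 3.1) counts participant management among the matters on which important protocol deviations are summarized, and the present wording leaves it arguable whether such dosing would be a deviation.

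**Working it through.** No arithmetic beyond counting applies. The check is a comparison of the texts.

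**1. Does the label reach the stops?** The sentence on suggestions covers the guidelines in Table 8 without limit. Only the following sentence, on site SOPs, is confined to treatment of the events. The table's title and the reference to it in 6.6.2 both put dose modification within its scope. The label therefore reaches the stop entries.

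**2. How many stops are there?**

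| Table 8 row | Permanent stop directed? | Times stated in the row | Excepted from the label? |
|---|---|---|---|
| Grade 1 | No | – | – |
| Grade 2 | Yes, if it occurs under adequate premedication | 1 | No |
| Grade 3 or 4 | Yes | 2 | No |

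Two of three rows direct a permanent stop, and 0 of those 2 are excepted. The Grade 3/4 stop follows a note on anaphylaxis in the treatment column, but the premedication column rules out further dosing for the whole row, so the stop is not limited to anaphylaxis.

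**3. Is the verb in the Grade 2 entry a separate weakness?** No. The same *should be* form is used for other permanent stops, in the general instructions to Table 6 and in Section 10.8.1.1 on liver rechallenge. It is the protocol's ordinary way of directing a stop.

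**4. Is Table 8 treated differently from its neighbour?** Section 6.6 has two dose-modification tables, 6 and 8 (Table 7 is a laboratory panel). Table 6 is introduced neutrally: "Dose modification and toxicity management guidelines for irAEs associated with immunotherapies are provided in Table 6". Only Table 8, 1 of 2, is introduced as suggestions.

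**5. Is the rule still in use?** Yes. Amendment 2 ended screening and feladilimab/placebo dosing, but participants may remain on pembrolizumab with 5FU-platinum. The pembrolizumab row of the Schedule of Activities allows up to 35 cycles and points to Section 6.6 and its subsections for unacceptable toxicity.

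**6. Which stop is exposed?** Mainly recurrent Grade 2. That row's default after a Grade 2 reaction is to carry on: restart at half the infusion rate if symptoms clear within an hour, otherwise hold and premedicate before the next scheduled dose. The stop is given once, in a separate paragraph after the list of measures. The Grade 3/4 stop is flat and repeated.

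**The case against.** The strongest reply is that the protocol already settles the matter. The note in Section 6.6 is parent text for every subsection and excepts no table. Section 7.1 and the Schedule of Activities both point into Section 6.6, Section 7.1 bars retreatment once treatment is permanently discontinued, and Section 8 allows no waivers. On this view the SOP sentence shows what was meant by suggestions: sites may vary acute care, and stops follow the general rule. Table 6 is also called guidelines, and its footnote b leaves some stops to the investigator, so it is not a uniformly binding comparator. The study is terminated, and nothing in the documents shows a site misreading the rule.

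Much of this stands. A careful reader will conclude that both stops bind, and no text permits re-dosing after a stop. The Grade 2 stop is a paragraph of its own, not one of the supportive-care bullets. The contrast with Table 6 is supporting evidence only, although footnote b shows that where discretion is wanted the protocol grants it entry by entry.

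It does not remove the conflict. The limit to treatment is in the second sentence and not in the first. The more specific statement, placed directly above the table, contradicts the general one. The bar on retreatment applies only after a participant has been discontinued, so it does not help a site that regards the discontinuation itself as optional.

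**Conclusion.** The concern holds: Section 6.6.2 is wrong as written. It is a wording conflict in a patient-safety rule that is still in use. It is not a missing stopping rule or a competing one.

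Its size is modest. Two stop entries are affected, and in practice the exposure is mainly to recurrent Grade 2 reactions among participants still receiving pembrolizumab. The documents give no infusion-reaction rate, so the number affected cannot be stated. Table 2 records no cytokine release syndrome in the GSK3359609 programs, but that is not an infusion-reaction rate for pembrolizumab. No efficacy endpoint, power figure or error rate is affected.

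The conclusion rests on reading the sentence on suggestions as covering the whole of Table 8, which its wording and the table's title support. The sponsor should correct it.

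**What to change.** In Section 6.6.2, reword the sentence before Table 8 so that the latitude to treat the table as suggestions and to follow site SOPs applies only to acute medical management and premedication. Add one sentence: the two permanent-discontinuation entries in Table 8 (Grade 2 occurring under adequate premedication; Grade 3 or 4) are mandatory in line with Sections 6.6 and 7.1.

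The cost is one sentence reworded and one added. Table 8 stays as it is, and no procedure is added.

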6.6.3. Management of Chemotherapy-related Toxicities

Refer to chemotherapy prescribing information/local label or standard practice guidelines for the management of chemotherapy-related AEs or potential safety-related issues; including resuming chemotherapy treatment and dose reductions following recovery of AE. If chemotherapy is being held due to a chemotherapy-related toxicity, treatment with GSK3359609/placebo and pembrolizumab may continue unless otherwise instructed (refer to Section 6.6.1).

